### Participants

**Recruitment Site and Sample Size.** We will recruit pregnant participants at BPPN, which provides services to over 800 families per year; services begin in pregnancy and include screening for risk factors and stressors and supportive home-based services. Consistent with the NIH-wide initiative to increase diversity in research, recruiting at BPPN ensures representation of women of color. Based on the previous *SMC* pilot studies, we expect that 30% who initially consent to the study will not complete the full 4 intervention sessions. We plan to enroll and randomize 78 participants to retain 60 (30 *SMC*, 30 waitlist control).

**Eligibility Criteria.** Inclusion criteria are: (1) English-speaking, (2) currently pregnant and after 12 weeks but before 30 weeks gestation to allow for study completion prior to expected delivery, (3) aged 18 and older, (4) a history of trauma and PTSD, (5) able to comprehend the study protocol, consent form and provide written consent, and (6) able to commit to a minimum of 4 weekly intervention sessions. Exclusion criteria are: (1) non-English-speaking, (2) less than 18 years of age, (3) those with psychotic conditions or developmental disabilities requiring guardianship, (4) those with high-risk pregnancies necessitating extended bedrest or inpatient care, and (5) those unable to commit to completing the intervention sessions.

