**Aim 2 Analyses.** To describe the observed variability in the data and test for differences between groups, a linear mixed model will be fit to each considered outcome at each post-baseline measurement. Each outcome will be modeled as a function of randomized group assignment and the baseline value of the outcome variable, both treated as fixed effects. Once the model is fit, a linear contrast based on the estimated model parameters will be constructed and used to test for the overall effect of random assignment using an approximate F-test as implemented by SAS PROC MIXED. A point estimate and corresponding confidence interval to quantify group differences will be provided. Subject-level covariates predictive of outcome and their interactions with randomized assignment, such as modality (in-person vs telehealth) will be added to the models as a series of supportive analyses. To evaluate the robustness of initial analysis results, these models will be moreover used to evaluate the group effect within subgroups. Analyses will be conducted using intent-to-treat. All tests will be two-sided and tested at a 0.05 nominal significance level. Standard diagnostic plots will assess model fit and transformations of variables may be considered to meet statistical assumptions.

**Aim 3 Analyses.** We will examine acceptability of the SMC by evaluating the percentage of completion and drop-out rates as compared to similar PTSD treatments and through analysis of the CSQ scores

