**Aim 4 Analyses.** We hypothesized that the effect of the intervention on PTSD symptomatology is mediated by emotion regulation and interpersonal sensitivity, that is, that there is a direct and indirect effect of the SMC on PTSD symptomatology. A generalized linear model-based approach will be utilized. After establishing the total effect of the SMC on PTSD symptomatology in the context of the unmediated model of Aim 2, the effects of the intervention on the theorized targeted mechanisms will be estimated. This will be followed by the conduct of a multiple regression analysis with each of the factors (considered one at a time) and the SMC as independent variables in the prediction of PTSD symptomatology. This approach allows for estimation of the direct and indirect effects. The 95% confidence intervals for mediated effects will be based on bias-corrected bootstrap methods, which uses the cumulative distribution functions of the bootstrap parameter estimates to determine the upper and lower endpoints of the confidence intervals. The percentages mediated of total effect of the SMC on PTSD symptomatology will be calculated. Additional analyses with interaction terms between the SMC with emotion regulation and interpersonal sensitivity will be conducted and compared.

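### Aim 4 fits the two mechanisms only in separate regressions, so if they act in parallel and correlate, their mediated shares overlap and an inactive mechanism can often be declared a mediator

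*Combined protocol and SAP*

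**What the plan says.** The paragraph on Aim 4 under Proposed Analysis starts from the hypothesis that "the effect of the intervention on PTSD symptomatology is mediated by emotion regulation and interpersonal sensitivity". After the total effect from Aim 2, it estimates the effect of the SMC on each mechanism. PTSD symptomatology is then predicted by "a multiple regression analysis with each of the factors (considered one at a time) and the SMC as independent variables", and the plan states that this yields the direct and indirect effects.

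On inference and reporting it says: "The 95% confidence intervals for mediated effects will be based on bias-corrected bootstrap methods", and "The percentages mediated of total effect of the SMC on PTSD symptomatology will be calculated".

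The one extension is this: "Additional analyses with interaction terms between the SMC with emotion regulation and interpersonal sensitivity will be conducted and compared". Those are products of arm and mechanism. They do not amount to a model in which the two mechanisms are entered together to separate their effects, and no other section supplies one. Nor does any section warn that the separate percentages overlap.

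**The concern.** The hypothesis names two mechanisms, both self-reported at the same post-intervention assessment (Table 2), and each outcome regression leaves one of them out. If the omitted mechanism affects PTSD and correlates with the included one within arm, the included mechanism's coefficient takes up part of that effect. Multiplied by the SMC effect on the included mechanism, this becomes an indirect effect that belongs in part to the other mechanism. Neither a larger sample nor baseline adjustment is designed to remove this.

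At stake is what Aim 4 can say about how the SMC works. A mechanism that only travels with the active one could be reported as a mediator with a sizeable percentage. Two overlapping percentages could also be read as parts of one whole. The Study Overview says that the knowledge gained will feed applications for further evaluation, so a misattributed mechanism could be carried forward.

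**Working it through.** The documents give no power, precision or error figure for Aim 4, so there is no planned figure to reproduce.

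**Inputs from the documents**
- Sample size: "We plan to enroll and randomize 78 participants to retain 60", 30 per arm (Participants). The simulations use 60.
- Level: two-sided 0.05 (Aim 2 Analyses).
- The SMC is expected to move both mechanisms: Addressing Perinatal PTSD names both as targets, and the Aim 4 hypothesis predicts that both fall.
- Guide to the size of that effect: Table 1, interpersonal sensitivity 17.73 to 10.11, SE 1.40, n = 56. The SD is 1.40 × √56 = 10.48, and the change is 7.62 / 10.48 = 0.73 SD. This is an uncontrolled pre-post change, so it serves only as a high value.

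**Assumptions**
- Correlation ρ between the mechanisms within arm: 0.3 to 0.7.
- SMC effect on each mechanism: 0.5, 0.6 or 0.73 SD.
- Parallel mechanisms: neither acts on the other.
- Mechanisms and outcome have a within-arm SD of 1.

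**Algebra.** Let a1, a2 be the SMC effects on the mechanisms and b1, b2 their own effects on PTSD. The separate fit for mechanism 2 estimates

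a2 × (b2 + ρ × b1) instead of a2 × b2.

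With a1 = a2, the two separate shares sum to (1 + ρ) times the true combined share. The sum passes 100% once the true combined share exceeds 1/(1 + ρ), that is 77%, 67% or 59% at ρ = 0.3, 0.5 or 0.7.

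*Mechanism 2 inactive* (a1 = a2 = 0.6, b1 = 0.6, b2 = 0, total effect 0.5). Its separate indirect effect is 0.6 × 0.6 × ρ = 0.108, 0.180, 0.252, or 22%, 36% and 50% of 0.5. The true value is 0.

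*Both active* (b1 = b2 = 0.35). The true combined share is 2 × 0.6 × 0.35 / 0.5 = 84%. The separate shares sum to 84% × (1 + ρ) = 109%, 126% and 143%.

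**Simulation, n = 60: how often the inactive mechanism is declared a mediator**

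| Rule and SMC effect on each mechanism | ρ = 0 | ρ = 0.3 | ρ = 0.5 | ρ = 0.7 | Joint model |
|---|---|---|---|---|---|
| Both paths p<0.05, 0.6 SD | not run | 17% | 40% | 57–58% | about 3% |
| Bias-corrected bootstrap, 0.73 SD | 7.5% | 33% | 64% | 78% | 6–9% |
| Bias-corrected bootstrap, 0.5 SD | 6% | 20% | 44% | 51% | 4.5–6% |

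The first row was rerun with 20,000 trials per case and agrees. The bootstrap rows follow the plan's interval method, with b1 = 0.6 and a true share of 80% through mechanism 1. They use 400 to 600 trials, so the Monte Carlo standard error is at most √(0.25/400) = 2.5 percentage points.

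**Limits of the effect**
- If the SMC does not move the inactive mechanism (ρ = 0.5, bootstrap), false declaration is 7%.
- If the true share is 40% rather than 80% (0.73 SD, ρ = 0.5), the estimated shares sum to more than 100% in 6% of trials, although the inactive mechanism is still declared in 66%.
- At ρ = 0 with an 80% share (0.73 SD), sampling noise alone takes the sum past 100% in 33% of trials. At ρ = 0.3, 0.5 and 0.7 it does so in 51%, 66% and 74%.

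**Cost of a joint model.** With one active mechanism, the SD of its indirect effect rises from 0.170 to 0.172, 0.175 and 0.184 (1–8%). With both active (slope 0.35, both-paths rule), the chance of declaring each real mediator falls from about 60/62/63% to 52/50/42% at ρ = 0.3/0.5/0.7. Part of the higher figure is effect borrowed from the other mechanism.

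**If the mechanisms form a chain.** Take an SMC effect of 0.8 SD on the upstream mechanism, a link of 0.7 to the downstream one and a final slope of 0.6. The true upstream indirect effect is 0.8 × 0.7 × 0.6 = 0.336. The separate fit returns 0.336 (declared in 79% of trials). The joint model returns about zero (declared in 4%).

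**The case against.** The strongest reply concerns causal structure. The joint model is right for parallel mechanisms, but the documents state no ordering. If emotion dysregulation drives interpersonal sensitivity, the separate fit is the correct one for the upstream mechanism. This stands: the separate fits should not be discarded.

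Second, a reader might infer that both mechanisms will be reported as mediators whenever either one is. The figures do not support that. In the both-paths simulation, among trials declaring at least one mechanism, both were declared in 17%, 40% and 62% at ρ = 0.3, 0.5 and 0.7. The problem also needs a correlation that the documents do not give, and it disappears at zero.

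Third, the plan does not say that the percentages will be added. That is so, and a sum above 100% is a possible misreading, not a planned result. But the plan does label the separate results as direct and indirect effects and percentages mediated, which goes beyond description.

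Fourth, Table 2 lists four instruments as theorized mechanisms (PHQ-9, STAXI-AX, SCL-90/IPS, DERS). If all are meant, a joint model with 60 participants would carry four mechanism regressors, and the loss of precision given here covers only two. This stands as a point to settle in the wording.

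Finally, Aim 4 is labelled exploratory, as are the hypotheses generally under Effect Size and Power Calculations. That lowers the weight of the point but does not make the separate estimates answer the question of which mechanism is at work.

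**Conclusion.** The point holds in a conditional form. If the SMC moves both mechanisms, and they act in parallel and correlate within arm, the planned separate indirect effects overlap. At an assumed correlation of 0.3 to 0.7 with 60 participants, a mechanism with no effect of its own is often, not always, declared a mediator: 17–58% of trials under the both-paths rule and 20–78% under the planned bootstrap, against about 3–9% jointly. The sum of shares exceeds 100% in expectation only when the true combined share is above roughly 59–77%.

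A reader might go on to infer that the separate fits are invalid, or that the trial's efficacy result is affected. Neither follows. The separate fits are correct for an upstream mechanism in a chain, and the Aim 2 comparison does not use the mechanisms. What is at risk is a misleading choice of mechanism for later work. A joint model also leaves other mediation assumptions, such as no unmeasured confounding, untouched.

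**What to change.** In Aim 4 Analyses:

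1. Add an outcome regression with arm and both mechanisms together. Name the instrument that represents each mechanism.
2. From it, report each specific indirect effect and the total indirect effect, with the bias-corrected bootstrap intervals already planned.
3. Base any statement about which mechanism carries the effect, or about the combined share, on this model.
4. Keep the one-at-a-time fits beside it, labelled as overlapping and not additive.
5. State that the joint specific effects assume parallel mechanisms, and that if one acts through the other, the separate fit gives the upstream mechanism's total indirect effect.

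This needs new wording and one more regressor, with no new data or visits. The price is lower power for each specific effect when both mechanisms are active, which is why the total indirect effect should be reported as well. The plan should state that loss.

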## RESEARCH ACTIVITIES

### Study Overview

To achieve these aims, we will conduct a pilot randomized controlled trial. For Aim 1, we will assess feasibility of the *SMC* intervention through tracking and close monitoring of participant engagement, accrual, and retention rates. For Aim 2, we will conduct baseline assessments for all participants for trauma, PTSD diagnosis and symptoms, affect regulation including depression, anger expression, dissociation, and emotion regulation, as well as interpersonal sensitivity. We will then randomize participants to either the *SMC* intervention group or to the waitlist control group. Those in the *SMC* intervention ( $n = 30$ ) will receive a minimum of 4 *SMC* modules and corresponding weekly sessions with an interventionist prior to completing the post-intervention assessment. Those in the waitlist control ( $n = 30$ ) will complete a post-intervention assessment at 6 weeks following their baseline assessment and will then be offered the *SMC* intervention. We will use intent-to-treat analyses to evaluate the preliminary efficacy of the *SMC* for reducing PTSD. For Aim 3, we will examine post-intervention indices of client satisfaction and evaluation of drop-out rates. For Aim 4, we will examine how changes in the theorized targeted mechanisms mediate the relationship between the *SMC* intervention and PTSD. We will utilize knowledge gained to prepare applications for continued evaluation of the impact and implementation of *SMC*. Prior to beginning any study activities, we will apply for approval with the Institutional Review Board (IRB) at the University at Buffalo and will require human subjects training for all study team members through the Collaborative Institutional Training Initiative (CITI Program).

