### Study Procedures

For Aim 1, we will maintain a master tracking file that indicates mode of invitation (handouts or flyers, word of mouth), screening and determination of eligibility, random assignment to *SMC* or waitlist control, receipt of informed consent, mode of delivery (in-person or by telehealth), and completion of assessments and intervention sessions. We will also track *SMC* uptake for waitlist controls, who will be invited to begin the *SMC* 6 weeks following baseline and immediately following the post-intervention assessment. We will enroll 3-4 participants per week (divided between intervention and control groups) during the active recruitment period.

For Aim 2, our procedures include baseline assessment for all participants, randomization to *SMC* or the waitlist control group, provision of a minimum of 4 *SMC* sessions for those in the *SMC* intervention arm, and post-intervention assessments (for both *SMC* and waitlist control groups).

For Aim 3, we will assess the acceptability of the *SMC* through post-intervention assessment feedback and through evaluation of lost-to-follow-up rates.

For Aim 4, we will examine how changes in the theorized targeted mechanisms mediate the relationship between the intervention and PTSD symptomatology, using the same assessment data utilized for Aim 2.

**Recruitment Strategy.** We will disseminate study information to all BPPN clients through informational handouts and fliers. Those interested will be invited to contact the licensed master social worker (LMSW) for screening. Women who meet all inclusion criteria and no exclusion criteria will be provided with a detailed explanation of the study, and will be encouraged to ask questions prior to providing written consent. They will then be invited to complete the baseline assessment with the LMSW. Once baseline assessment is completed, participants will be: 1) randomized to the *SMC* or waitlist control arm in a 1:1 fashion using a block randomization scheme, 2) will be mailed the *SMC* materials and 3) be assigned to the community health

worker (CHW) who will contact the participant and arrange the first session, either in-person or remotely according to the participant's preference. Consent forms will outline remuneration for each aspect of the study (\$30 for the baseline and \$40 for the post-intervention assessments).

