## Measures

We plan to use reliable and valid measures, these and their schedule of use are listed in **Table 2**. For **eligibility screening** we will use the 5 sentinel items from the Childhood Trauma Questionnaire (CTQ), and the Primary Care PTSD Screen for DSM-5 (PC-PTSD-5). For the **baseline assessment** we will assess trauma exposures, PTSD and its dissociative subtype, and measurements related to the theorized mechanisms of change, including for affect regulation and interpersonal sensitivity. All of these will be repeated at the **post-intervention assessment**. Also, at post-intervention, participants in the SMC arm will complete the

Client Satisfaction Questionnaire (CSQ-8), and invite feedback regarding perception and experience of in-person vs telehealth sessions based on their choice of modality. For those in the SMC arm we will utilize two measures during each weekly intervention session: SMC fidelity checklists, as well as Subjective Units of Distress (SUD). The SUD will be assessed on a 0-10 scale by asking the participant to rate any distress experienced ahead of session, at mid-session, and at the close of the session. Those with SUD rating of 5 or above at the session's end will be encouraged to participate in a brief relaxation exercise until their rating is reduced to 4 or lower. All who complete baselines and are randomized will be scheduled for the post-assessment; those who fail to complete will be scheduled based on their anticipated completion date.

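### Aim 4's outcome regression lists only one mechanism and arm; baseline PCL-5 and that mechanism's baseline score should be in all three Aim 4 models

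*Combined protocol and SAP*

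**What the plan says.** All references are to the combined protocol and SAP.

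- **Total effect.** Aim 4 Analyses begins "After establishing the total effect of the SMC on PTSD symptomatology in the context of the unmediated model of Aim 2". Aim 2 Analyses defines that model: "Each outcome will be modeled as a function of randomized group assignment and the baseline value of the outcome variable".
- **Arm to mechanism.** Aim 4 says these effects will be estimated and names no covariates. Aim 2 says "a linear mixed model will be fit to each considered outcome", which may or may not include the mechanism scores.
- **Mechanism and arm to PTSD.** This is a multiple regression "with each of the factors (considered one at a time) and the SMC as independent variables in the prediction of PTSD symptomatology". No baseline score is named.
- **Summary measure.** "The percentages mediated of total effect of the SMC on PTSD symptomatology will be calculated". Confidence limits are bias-corrected bootstrap.
- **Data available.** The Study Overview lists baseline assessment of "affect regulation including depression, anger expression, dissociation, and emotion regulation, as well as interpersonal sensitivity". Of the baseline measures, the Measures section says "All of these will be repeated at the" post-intervention assessment. Table 2 places PCL-5, DERS and SCL-90/IPS at those two visits only. Study Procedures says Aim 4 will be done "using the same assessment data utilized for Aim 2".
- **Status.** Proposal Aims calls Aim 4 exploratory, and the power paragraph says the same of the study's hypotheses.

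**The concern.** Arm is randomised; the mechanism score is not. A participant with more severe symptoms at entry will tend to score higher on both the mechanism and PTSD at post-test. If the outcome regression holds neither baseline score, that shared severity enters the mediator slope. The slope is multiplied by the arm effect on the mechanism to give the indirect effect, so an intervention that lowers both scores by separate routes can appear to lower one through the other.

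Aim 4 exists to say whether emotion regulation and interpersonal sensitivity carry the effect on PTSD. Two analysts following the text could fit different models and reach different answers, although the scores needed for adjustment are already collected.

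**Working it through.** The plan gives no effect size, correlation or sample size for Aim 4, so there is no figure to reproduce. The check is algebra plus simulation.

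**Inputs from the plan.** 60 retained, 30 per arm (Recruitment Site and Sample Size); two-sided 0.05 (Aim 2 Analyses); bias-corrected bootstrap limits (Aim 4 Analyses).

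**Assumed inputs.** Standardised scores with within-arm variance 1. M is the mechanism, Y is PTSD, 0 is baseline, 1 is post-test, T is arm:

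M1 = s·M0 − a·T + e1; Y1 = s·Y0 − 0.6·T + e2

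Here corr(M0, Y0) = r, s is pre-post stability, corr(e1, e2) = ρ, and a = 0.6 unless stated. M1 does not enter the equation for Y1, so true mediation is zero.

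**Step 1: slope as listed.** Given arm, cov(M1, Y1) = r·s² + ρ(1 − s²) and var(M1) = 1. With ρ = 0 the slope is r·s²: 0.3 × 0.25 = 0.075; 0.5 × 0.25 = 0.125; 0.6 × 0.36 = 0.216. Simulated mean slopes were 0.071, 0.135 and 0.218. With both baselines in the model, the slope is ρ.

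**Step 2: false-positive mediation, ρ = 0** (1,000 replicates, 500 bootstrap draws each; Monte Carlo SE about 0.9 points near 8%).

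| r / s | As listed | Median % mediated, as listed | Baseline PTSD kept, mediator adjusted for its own baseline | Both baselines in all models |
|---|---|---|---|---|
| 0.3 / 0.5 | 10.7% | 5% | 7.6% | 8.3% |
| 0.5 / 0.5 | 16.8% | 11% | 8.5% | 7.6% |
| 0.6 / 0.6 | 33.1% | 19% | 7.7% | 7.8% |

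In the last two columns the median mediated is under 1%. Part of the excess over 5% there comes from the bias-corrected interval: with both baselines, percentile limits gave 4.3%, 3.9% and 3.6%.

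**Step 3: smaller effect on the mediator.** With a = 0.3, the as-listed rate is 6.2% at 0.5/0.5 and 14.1% at 0.6/0.6.

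**Step 4: baseline mediator also predicts later PTSD** (assumed coefficient 0.2, ρ = 0; 0.5/0.5 and 0.6/0.6). Keeping baseline PTSD alone gives 13.4% and 17.8%, with 7% to 8% mediated. Both baselines give 7.9% and 7.4%, with about 0%.

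**Step 5: total against direct plus indirect.** With least squares and an unadjusted arm-to-mechanism step, direct plus indirect as listed equals the unadjusted arm difference. The Aim 2 total is the adjusted difference. Under randomisation both have the same expectation, so the gap has mean zero. Its median absolute size was 14.0%, 15.0% and 17.3% of the true effect, or 0.084, 0.090 and 0.104 SD (each × 0.6). It was about 1% with baseline PTSD kept, and exactly zero with common covariates and participants.

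**Step 6: correlated post-test errors.** At ρ = 0.3 the as-listed rates are 53.0%, 59.3% and 67.4%; with both baselines they are 57.2%, 57.3% and 62.4%, with 28% to 30% mediated. At ρ = 0.5 they are 69.6%, 70.2% and 71.2% as listed, against 77.3%, 77.3% and 83.1% with both baselines. Adjustment sharpens the estimated arm effect on the mechanism, and the slope stays at ρ.

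**The case against.** The best defence is that calling Aim 2 the unmediated model implies its ordinary counterpart: the same model plus the mediator, with baseline PTSD kept. Aim 2's adjustment of each outcome for its own baseline can be extended to the mechanism step. On that reading the bias is already near zero with independent errors, and the fix changes little unless Step 4 applies. This stands, and it limits the size of the point. It does not remove it, because the sentence describing the regression lists two terms and stops.

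The aims also speak of changes in the mechanisms, which could mean change scores. As listed, a change-score mediator has slope −r·s/2 when ρ = 0 (−0.075, −0.125 and −0.18 in the three settings), so the bias reverses sign. With baseline PTSD kept, simulated rejection was 5% to 10% and the median mediated about 0% to 1%. The direction of the as-listed error therefore depends on a definition that the plan does not give.

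Three stronger readings are tempting, and the documents do not support them:

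- A reader might infer that the mismatch with the Aim 2 total makes the percentage mediated systematically wrong. Step 5 shows that the gap is chance baseline imbalance. The percentage can still be computed; the systematic error is in the slope.
- A reader might infer that baseline adjustment makes Aim 4 a sound test of mechanism. Step 6 shows otherwise.
- A reader might infer that same-visit measurement is a fault peculiar to this plan. It is a general limit of two-visit mediation analysis, and the plan calls the aim exploratory.

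**Conclusion.** The point holds as a moderate one, for consideration. If the regression is fitted with only the terms listed and the post-test score as mediator, shared baseline severity biases the mediator slope. False-positive mediation is then about 11% to 33%, with a median of 5% to 19% spuriously mediated, for r/s from 0.3/0.5 to 0.6/0.6. It is less if the intervention has a small effect on the mechanism. If baseline PTSD is kept, the rate is about 7% to 9% and the bias is near zero, subject to Step 4.

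These figures rest on assumed correlations, stabilities and effects, and on independent post-test errors. Two facts need no assumption: the listed terms differ from those of the model that supplies the total, and mediator and outcome come from the same post-test visit. No stated decision depends on the percentage mediated, and Aims 1 to 3 are unaffected.

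**What to change.** In Aim 4 Analyses:

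1. Define the mediator as the post-test mechanism score.
2. Name one covariate set, baseline PCL-5 and the baseline value of that mediator, for all three models: arm on PTSD; arm on mediator; arm and mediator on PTSD.
3. Fit all three on the same participants and take the total effect from that set, so that total equals direct plus indirect. The Aim 2 estimate stays as it is.
4. State that this removes confounding by the measured baseline scores only, and that mediator and PTSD share a visit. Report a positive result as consistent with mediation, not as evidence of mechanism.

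Optionally, add a table of the indirect effect over assumed residual correlations, for example 0 to 0.5, with the value at which it reaches zero.

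The cost is a few sentences in the SAP and two degrees of freedom per model. No new data or visits are needed.
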